## 1.0 Objectives

The overarching goal of this proposal is to understand the comparative effectiveness of obesity counseling as covered by Centers for Medicare and Medicaid Services (CMS) in improving weight loss for adults either with or at high risk of type 2 diabetes. CMS and most insurers now include obesity screening and counseling benefits, with no cost sharing to patients. Since overweight patients are at highest risk for diabetes, improved weight management services could prevent diabetes and its negative health outcomes. Beneficiaries with obesity are eligible for up to 20 face-to-face visits for weight counseling in the primary care setting. We propose comparing weight and diabetes outcomes in three states using electronic health record (HER) and claims data before and after this policy was implemented. The PaTH network brings together six academic health systems – the University of Pittsburgh/University of Pittsburgh Medical Center, Penn State College of Medicine/Hershey Medical Center, Temple University School of Medicine/Temple Health, and the Johns Hopkins University/Johns Hopkins Health System/Johns Hopkins Health Care, Geisinger Health Systems, and The University of Utah – to function as an integrated research network and learning health system, providing an infrastructure for observational studies, such as the one proposed here, that require populations beyond a single health system to answer important patient-centered health services questions ([www.pathnetwork.org](http://www.pathnetwork.org)). Using the PaTH Clinical Data Research Network (CDRN) infrastructure, we propose the following specific aims:

**Aim 1: Evaluate the impact of universal preventive service coverage for obesity screening and counseling on weight loss, diabetes incidence, and diabetes outcomes, in patients with diabetes or at high risk for diabetes (defined by body mass index (BMI)  $\geq 25$ ).** We will determine how the annual probability of receiving obesity and/or nutritional counseling (as defined by Current Procedural Terminology (CPT) code) changed pre- and post-policy across all insurers in a cohort of patients with diabetes and at high risk for diabetes. We hypothesize that individual patients are more likely to receive counseling following coverage implementation. Further, we hypothesize that patients who receive a greater number of face-to-face visits will have greater weight loss compared to those who receive fewer visits.

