Diabetes Service Use	-Clinic visit with primary or secondary diagnosis of diabetes -Emergency department visit with primary or secondary diagnosis of diabetes -Hospitalization with primary or secondary diagnosis of diabetes	Available at all PaTH sites
Exposure variables		
Individual level	-Sociodemographics (e.g., age, sex, race, insurance status, rural vs. urban) -Medical co-morbidities	Available at all PaTH sites
Provider/practice level	-Practitioner type (advanced practice vs. MD/DO) -Practitioner specialty -Practice size (# of providers) -Practice type (multispecialty, academic) -Practice setting (rural vs. urban)	To be determined

**Data Transfer.** The PaTH network has established an operational data infrastructure with the necessary technical safeguards as agreed upon in the PaTH Data Use Agreement (DUA) for sharing and analyzing data while addressing data confidentiality and security concerns. PaTH has deployed two mechanisms for storing, protecting, and sharing data (as described previously under PaTH Governance and Regulatory Issues): (1) data with PHI are stored and protected behind each institution's firewall in the distributed data network and (2) de-identified data are sent to the PaTH data center at

the University of Pittsburgh (CERC-DC). Once data integration is accomplished at each site, sites will remove all PHI and send the de-identified version of the integrated data to the CERC-DC through PaTH's virtual private network/secure file transfer protocol (VPN) which has been operational for data transmission since November 2014. Data analysis can then be performed via secure remote computing using standard statistical software packages (e.g., SAS). This model ensures that the highest level of privacy and confidentiality for the data that are maintained at each site, the CERC-DC, and at Penn State.

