## 8.0 Statistical Plan

Descriptive statistics will be generated to describe the characteristics of different cohorts of interest. The diabetes related outcomes will be summarized at the individual level on a yearly basis. There will be binary outcomes (Yes/No) such as controlled diabetes, controlled blood pressures, receiving annual eye exam, receiving obesity and/or nutritional counseling, and count outcomes such as numbers of clinic visits, emergency department visits and hospitalization, and continuous outcomes such as cost of healthcare utilizations. The distributions of outcome measures will be examined by using minima, maxima, ranges, medians, quartiles, means, and standard deviations for continuous variables, and frequency and contingency tables for categorical variables.

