where  $\mathbf{x}_{mijk}$  is the vector of regressors for the fixed effects,  $\boldsymbol{\beta}_m$  is the corresponding vector of fixed-effects parameter coefficients,  $\mathbf{z}_{ij}$  is a vector of cluster-level regressors for the random effects for the  $j^{\text{th}}$  cluster of the  $i^{\text{th}}$  state,  $\boldsymbol{\gamma}_{1ij}$  is the cluster-level random-effect coefficients and is common to all  $m$ , and  $\boldsymbol{\gamma}_{2mijk}$  is the subject-level random-effect coefficients associated with the parameter  $\beta_m$  for the  $k^{\text{th}}$  subject within the  $j^{\text{th}}$  cluster. The random effects are assumed to follow a multivariate normal distribution with mean zero. Because the vector  $\mathbf{x}_{mijk}$  may include subject-level, cluster-level and state-level exposure variables, the fixed effects parameter vectors  $\boldsymbol{\beta}_1$  and  $\boldsymbol{\beta}_2$  represent the effects of different exposure variables on the annual changes in the pre- and post-periods. Thus, we may perform statistical tests to examine whether there are differences in trends between the pre- and post-periods overall and for each state, and whether the patterns of changes differ between the states.

Similarly for a count outcome  $Y_{ijkt}$  (e.g., number of clinical visits), we define the expected value  $\mu_{ijkt} = E(Y_{ijkt})$  and apply a Poisson regression model based on the natural log link function. The log expected number of clinical visits,  $\log(\mu_{ijkt})$ , can be modeled with the aforementioned segmented mixed-effects model. The use of an offset term in the models yields the estimates of the rate of clinical visits rather than the mean number of visits. The fixed-effect parameters,  $\beta_1$  and  $\beta_2$ , represent the effects of exposure variables on the annual changes in log of incidence rates for the pre- and post-periods, respectively. For a continuous outcome  $Y_{ijkt}$ , we will model the mean,  $\mu_{ijkt} = E(Y_{ijkt})$ , with the mixed-effects model and the parameters  $\beta_1$  and  $\beta_2$  indicate the effects of exposure variables on the annual changes in the outcomes for the pre- and post-periods, respectively. All final statistical models will be assessed with respect to the goodness-of-fit and the appropriateness of model assumptions. Statistical software SAS 9.4 and R environment will be used to implement the proposed analyses.

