Furthermore, we will use the similar models as described above to evaluate post-policy impact of obesity screening and counseling (number of visits) on the outcomes such as weight loss, diabetes incidence, and diabetes outcomes (including hemoglobin A1c, controlled blood pressure, use of a statin medication). The outcome data collected after the universal coverage change (i.e.,  $t = 0, 1, \dots, 6$ ) will be used to estimate the trend of change. The number of screening and counseling will be used as a predictor in the mixed effects models. The effects of patient and practice characteristics will also be examined in the models. Statistical software SAS 9.4 and R environment will be used to implement the proposed analyses.

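### In the diabetes cohort, the clinic-visit outcome can include the counseling visits that are the exposure, so a post-policy change in it need not mean a change in other diabetes care

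*Combined protocol and SAP*

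**What the plan says.** **Outcome.** For the diabetes cohort, Table 1 in section 7.2 lists Diabetes Service Use with three components. The clinic component is "Clinic visit with primary or secondary diagnosis of diabetes". No procedure code or visit type is excluded, in Table 1 or in section 8.0.

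**Exposure.** Section 1.0 describes the covered service: "Beneficiaries with obesity are eligible for up to 20 face-to-face visits for weight counseling in the primary care setting". Counseling is identified "as defined by Current Procedural Terminology (CPT) code", and Aim 1 expects it to increase: "We hypothesize that individual patients are more likely to receive counseling following coverage implementation".

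**Analysis.** Section 8.0 lists "count outcomes such as numbers of clinic visits, emergency department visits and hospitalization". It then uses clinical visits as the worked example for the segmented Poisson mixed model, where the offset "yields the estimates of the rate of clinical visits rather than the mean number of visits". Receipt of counseling is listed separately as a binary outcome. In the later post-policy analysis, "The number of screening and counseling will be used as a predictor in the mixed effects models". The outcomes given there as examples are weight loss, diabetes incidence, A1c, blood pressure and statin use.

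**The concern.** The outcome is defined by diagnosis and the exposure by procedure code, so one visit can satisfy both. Every patient in this analysis has type 2 diabetes. If diabetes is recorded at a counseling visit, even as a secondary diagnosis, that visit counts as diabetes service use. It may also register as uptake of counseling, which the plan treats as a different outcome.

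Section 8.0 proposes to read the change in slope after the policy as the policy's impact. A single total cannot tell apart three things: added counseling visits, counseling that replaced ordinary visits, and a change in other diabetes care. A rise could be reported as more diabetes care when it is only uptake of the benefit, and a fall in other visits could be hidden behind it.

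**Working it through.** The plan gives no visit rate, uptake, effect size, alpha or power for this outcome, so there is no figure of its own to reproduce. As an input check, the five site counts of patients with diabetes in section 7.2 sum to the stated total: 25,219 + 150,589 + 60,324 + 40,536 + 51,787 = 328,455.

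**Inputs (all assumed; the documents give none)**
- m: other diabetes-coded clinic visits per patient-year
- u: share of the cohort counseled
- v: counseling visits per counseled patient per year (the documents give only the cap of 20)
- q: share of counseling visits that carry a diabetes diagnosis
- s: counted ordinary visits displaced per counseling visit

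**Policy contrast, no effect on other care.** Rate ratio = 1 + u·v·(q − s)/m.
- m = 3, v = 3, q = 1, s = 0: u = 1% gives 1 + 0.03/3 = 1.01; u = 5% gives 1 + 0.15/3 = 1.05.
- q = 0 with s = 0, or s = q: 1.00. If s exceeds q, the ratio is below 1.
- m = 4, u = 5%, v = 6, s = 0: 1.019, 1.038 and 1.075 for q = 0.25, 0.5 and 1.
- Over m = 2-4, u = 1-20%, v = 2-20, q = 0-1 and s = 0, the ratio runs from 1.00 to 3.00. The top needs 20% uptake with every patient at the 20-visit cap.

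These are comparisons of level. The model in section 8.0 has two slopes meeting at the policy year and no separate level term. Extra counted visits would therefore load on the post-policy slope, by an amount that depends on how uptake builds up.

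**Counseled versus not counseled, no effect on other care.** Rate ratio = 1 + v·q/m.
- m = 3, v = 3: 2.0 if q = 1; 1.5 if q = 0.5.
- m = 4, v = 6: 1.38, 1.75 and 2.50 for q = 0.25, 0.5 and 1.

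This contrast arises only if the counseling-visit predictor is applied to clinic visits.

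**Could a small overlap reach significance?** A rough smallest detectable ratio is exp[(1.96 + 0.84)·√(2φ/(N·m))], with two-sided 5% and 80% power assumed. With N = 328,455, m = 2-4 and overdispersion φ = 1-10, it is about 1.003-1.016. This ignores clustering and within-patient correlation, tests a level rather than a slope, and uses the site-table total before the visit-or-claims restriction. It shows only that a ratio of 1.01-1.05 is not obviously too small to be declared significant.

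**Effect of simply excluding counseling-coded visits.** Section 2.1 dates the CMS code for intensive behavioral therapy (IBT) for obesity to 2012, while section 7.2 starts data in 2009. Suppose the 0.15 visits per patient-year (5% × 3) are ordinary diabetes visits now billed with that code. The excluded count then falls from 3 to 2.85, a ratio of 2.85/3 = 0.95, with no change in care.

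**The case against.** A reader might infer that clinic use must rise with coverage by construction. The documents do not support that. They do not say which diagnoses counseling visits carry, and a visit coded for obesity alone is not counted. Counseling in the same clinic may also replace a visit that would have been counted anyway.

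A reader might also take ratios of 2 or more between counseled and uncounseled patients, or (3 + 20)/3 = 7.7 at the cap, as the size of the problem. Neither Aim 2 nor the post-policy analysis in section 8.0 names clinic visits for that contrast. Only an open-ended list leaves room for them, and a cap on eligibility is not observed use.

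Further, total diabetes-coded clinic use is a legitimate policy outcome, because the added visits are real utilization. The plan nowhere hypothesizes a fall in other visits. Section 8.0 already asks the investigators to judge the clinical significance of each significant result. And excluding counseling-coded visits can create its own artifact.

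Most of this stands. It limits the size and certainty of the point and rules out replacing the total. It does not remove the overlap: the definition admits counseling visits, the clinic count is explicitly modeled against the policy, and nothing separates the two. Judging clinical significance would not show where a change came from.

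**Conclusion.** The point holds as a possible overlap of unknown size, not as a demonstrated bias. It concerns one component of one Table 1 outcome, in the diabetes cohort only, and this outcome is not among those named in the aims. Emergency visits and hospitalizations do not share the problem.

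The cohort-wide ratio of about 1.01-1.05 rests on 3 other visits a year, 1-5% uptake, and 3 counseling visits that are all additional and all coded with diabetes. It is 1.00 if none are so coded or if they fully replace ordinary visits. The counseled-versus-uncounseled contrast would be affected more, but only if the plan extends that model to clinic visits. As written, a slope change in clinic visits cannot be assigned to diabetes care other than counseling.

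**What to change.** In Table 1, keep total diabetes-coded clinic visits and add two counts:
1. diabetes-coded clinic visits without any obesity or nutritional counseling code;
2. counseling-coded visits alone.

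In section 8.0:
- Fit the segmented model to the total and to the counseling-excluded count, and show the results side by side.
- Attribute a change to diabetes care other than counseling only if the two agree.
- If the number of counseling visits is ever used as a predictor of clinic visits, use the counseling-excluded count as the outcome.
- State that neither count is to be reported alone, because relabelling of ordinary visits from 2012 can lower the excluded count after the policy.

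The total minus the excluded count, divided by the counseling-coded count, also estimates the share of counseling visits coded with diabetes, which is the main unknown above.

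The cost is two lines in Table 1, a filter on codes that must be extracted anyway to define the exposure, and one additional model fit. A visit combining counseling with diabetes care drops out of the excluded count but stays in the total.

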***Diabetes Cohort Definition.*** During year 1 of the proposed project, the investigative team, in collaboration with the PaTH Network, will identify a valid cohort of patients with type 2 diabetes. The cohort of patients under study will be defined as all patients age 18 and older with an indication of type 2 diabetes during the proposed study time frame. Patients will be classified as having diabetes using a clinically validated algorithm: type 2 diabetes mellitus on the problem list, diabetes-specific medications, hemoglobin A1c (HbA1c) results > 7.0%, or one inpatient diagnosis code or two outpatient diagnosis codes for type 2 diabetes (ICD-9 codes 250.xx). The diabetes cohort will be further limited to patients who will likely be captured in the PaTH EHR records or claims data so that outcome assessments can occur. Thus, we will further limit the diabetes cohort to patients who have either: (1) had at least 2 outpatient primary care visits in one of the PaTH health systems in the past 3 years (since January 1, 2012), or (2) for whom claims data are available. The cohort will be dynamic, with new patients added into the cohort after 2015 as they meet the diabetes cohort definition prospectively. The observational period for the outcome variables will be for the 10-year period from 2009-2019, thus including 3 years of data prior to the first policy change (CMS instituting coverage for intensive behavioral therapy for obesity) and 3 years after the last policy change (Pennsylvania Medicaid expansion) under study.

Following the definition of the diabetes cohort and key diabetes outcomes and covariates as described above, an initial extraction of variables will be conducted in Year 2 of the proposed project for years 2009-2015. This early data extraction from the PaTH Network will allow for cohort validation and data cleaning and editing, as well as required programming and determination of the analysis models. We will utilize this initial data extraction in Years 2 and 3 to analyze the impact of early health policy changes, as well as to prepare a manuscript of both the protocol and early findings of policy impact. The final data extraction will occur during the final quarter of Year 4 of the proposed project, allowing for completion of a ten-year time period (2019).

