## Propensity scores matching

In the proposed modeling framework above, we adjust for the subject-level and cluster-level differences by including the exposure variables at different levels as covariates in the models. We also will consider a secondary analysis with a propensity scores matching approach to adjusting for these differences. A wide array of patient measures in the EHR, including demographics, insurance coverage, medical co-morbidities, health behaviors, and information on use of health care services, will be used to calculate the propensity scores. Propensity score-based stratification analysis will be performed to evaluate the overall impact of health policy using the modeling framework similar to that described above.

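### The counseling models name no baseline medication covariate, so drug-treatment differences in weight and A1c can be credited to, or held against, counseling

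*Combined protocol and SAP*

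**What the plan says.** The sentence that fixes the adjustment set is in Section 8.0, under Propensity scores matching. In the main modeling framework, "we adjust for the subject-level and cluster-level differences by including the exposure variables at different levels as covariates in the models". The exposure variables are listed at the end of Table 1 in Section 7.2. At individual level they are "Sociodemographics (e.g., age, sex, race, insurance status, rural vs. urban) -Medical co-morbidities". The provider and practice rows cover practitioner type and specialty, and practice size, type and setting.

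The paragraph of Section 8.0 on the post-policy effect of counseling enters the number of visits as a predictor of weight loss, diabetes incidence and diabetes outcomes including A1c. On adjustment it says only: "The effects of patient and practice characteristics will also be examined in the models".

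Medication appears elsewhere in the plan, in other roles. The diabetes algorithm (Sections 3.1 and 7.2) uses "type 2 diabetes mellitus on the problem list, diabetes-specific medications" among its criteria. Table 1 takes the statin outcome from the current EHR medication list, marked as available at all sites. It also names patient-reported medication reconciliation as a secondary outcome at some sites.

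**The concern.** Patients who are counseled, or counseled more often, are selected by their own and their clinicians' decisions. Treatment at that moment (insulin, several diabetes drugs, or another drug that alters weight) reflects how severe the disease is, and it also moves weight and A1c. If it differs between counseling groups, it is a confounder. A co-morbidity code does not replace it, because an untreated patient and one on insulin can both carry a code in the 250.xx range.

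Two comparisons are exposed: the counseled-versus-not contrast of Aim 2 and the more-versus-fewer-visits hypothesis of Aim 1. The Statistical Power paragraph expects very small effects to be detectable and relies on clinical judgment to sort significant results. That judgment can ask whether a difference is large enough to matter. It cannot tell a confounded difference from a real one.

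**Working it through.** **1. Is medication in the adjustment set?** Reading the covariate sentence, Table 1 and the counseling paragraph together, the individual-level set is sociodemographics plus co-morbidities. The "Sociodemographics (e.g., age, sex, race, insurance status, rural vs. urban) -Medical co-morbidities" entry has its only open-ended wording inside the sociodemographics bracket, so that wording does not extend to drugs.

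**2. Does another part of the plan deal with it?**
- Section 3.2 excludes only patients under 18.
- The named subgroups concern insurance, new enrollment, gender, age and race-ethnicity.
- Time-dependent covariates are mentioned as something mixed models can handle, but none is named.
- The counseling models use only data from after the coverage change (t = 0 to 6), so the segmented model's control for pre-policy level and trend does not operate there.
- Subject-level random effects do not remove confounding by a variable that is associated with the exposure.

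**3. Which outcomes are affected?**
- *Weight:* both cohorts, through any weight-altering drug; diabetes drugs matter chiefly in the diabetes cohort.
- *A1c:* the diabetes cohort.
- *Diabetes incidence:* not through diabetes drugs. A patient taking one already meets the diabetes definition and cannot become an incident case.

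**4. Scale.** The plan states no alpha, SD, effect size, share counseled or drug-use figure, so there is no design figure to reproduce. Its site counts do add up: 25,219 + 150,589 + 60,324 + 40,536 + 51,787 = 328,455 patients with diabetes. Every other input below is an assumption.

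Bias ≈ (drug effect on the outcome) × (difference in drug use between groups that remains after adjustment).

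| Assumed drug effect | Difference 2 points | Difference 10 points | Difference 20 points |
|---|---|---|---|
| −5 kg | −0.10 kg | −0.50 kg | −1.00 kg |
| −2 kg | −0.04 kg | −0.20 kg | −0.40 kg |
| +4 kg | +0.08 kg | +0.40 kg | +0.80 kg |
| −0.5 A1c points | −0.01 | −0.05 | −0.10 |
| −1.5 A1c points | −0.03 | −0.15 | −0.30 |

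The A1c rows show only the direct drug effect. Treatment as a marker of severity pulls the other way, so the net sign is not known.

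**5. Comparison with sampling error.** Take the diabetes cohort, 5% counseled and an SD of weight change of 10 kg (both assumed). Then n1 = 0.05 × 328,455 ≈ 16,423 and n0 ≈ 312,032. SE = 10 × √(1/16,423 + 1/312,032) ≈ 0.080 kg. A bias of 0.2 kg is then about 2.5 standard errors. With no true counseling effect, a two-sided 5% test would reject about 70% of the time. With 1% counseled the SE is about 0.175 kg, and biases of 0.2 kg and 0.5 kg would be declared significant about 21% and 81% of the time. These figures ignore clustering and repeated measures, and a realistic SE would probably be larger.

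**The case against.** The strongest reply is that medication is unspecified and not excluded. The propensity-score list is introduced as a wide array of EHR measures "including demographics, insurance coverage, medical co-morbidities, health behaviors, and information on use of health care services", which is illustrative wording. Section 7.2 also leaves the analysis models to be settled after the first data extraction. This stands for the propensity score. A reader might infer that both covariate lists wrongly leave out drugs, but the documents do not support that: the propensity list is open, the analysis is secondary, and its stated aim is different ("Propensity score-based stratification analysis will be performed to evaluate the overall impact of health policy"). It is not itself in error. The reply does not rescue the counseling models. Their adjustment set is tied to Table 1, and nothing commits the later model-building step to add medication.

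Three further objections are sound and narrow the point.
- *Size.* Every input is assumed. Applying a full drug effect to weight change overstates the bias for a long-stable drug, which mainly affects weight level. Table 1 defines weight loss from first to final IBT visit, which exists only for counseled patients, so a counseled-versus-uncounseled figure presupposes a measure that Table 1 does not define. Nor can an A1c threshold alone stand for uncontrolled diabetes, because Table 1 also counts a missing A1c as uncontrolled.
- *Data.* The documents show diabetes medications used for cohort entry and statins read from a current list. They do not show that dated histories, drug classes or other weight-altering drugs are extracted.
- *Statistical cost.* The cohort is dynamic, and one route into it needs only two primary care visits in three years. Some patients will lack a full look-back.

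**Conclusion.** The point holds for the counseling models of Section 8.0. Followed as written, they adjust for no drug treatment, so treatment differences can bias the estimated effect of counseling on weight in both cohorts and on A1c in the diabetes cohort. This rests on one assumption the documents can neither confirm nor refute: that drug use at the start of counseling still differs by counseling status once the listed covariates are accounted for.

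The size and direction are unknown. The assumed ranges, roughly −1.0 to +0.8 kg and up to 0.3 A1c points from the direct drug effect, show only that a bias of practical interest is possible and would not shrink with sample size. A reader might infer that bias has been demonstrated, or that diabetes drugs also confound incidence. The documents support neither. The first lacks inputs, and the second conflicts with the plan's own diabetes definition. The change should be made before the counseling models are run; it does not call the study design into question.

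**What to change.** For the counseling models, add medication before the index date to the individual-level exposure variables of Table 1 and refer to it in Section 8.0:
- *Diabetes cohort, weight and A1c:* insulin (yes/no), and number and class of other diabetes drugs.
- *Both cohorts, weight:* other weight-altering drugs, where the EHR medication list or claims supply them.
- *Index date:* the first counseling visit, or a matched date for uncounseled patients, with a stated look-back such as 12 months. Flag patients without the full look-back; do not code them as untreated.
- *Incidence model:* do not adjust for diabetes drugs, which are part of the outcome definition.
- *Drugs started after the index date:* do not adjust for them, since they may follow from counseling. Handle them only in a sensitivity analysis, for example ending weight follow-up at the first new start in both groups, and state that this censoring may be informative.
- *Propensity score:* if one is built for counseled versus uncounseled patients, include the same variables.

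The cost is plan wording, derivation of dated medication variables (possibly a wider extraction than the documents now show), some missing look-back data, and programming for one sensitivity analysis.
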